Data will be entered and analyzed on SPSS version 22. Percentages and frequencies will be calculated for the demographic variables of the patients. The comparison of the two groups will be made by using T- test. P-value of less than 0.05 will be considered significant and the power used will be 0.80.

RESULTS

Frequency and percentage of demographic data

Variables		Frequency	Percentage	
Gender	Male	105	58.7	
	Female	74	41.3	
Income	Less than	108	60.3	
status	50000			
	50000 -150000	69	38.5	
	Greater than	2	1.1	
	150000			
	Normal	166	92.7	
BMI	Obese	13	7.3	
	None	136	76.0	
Comorbidity	HTN	33	18.4	
	Diabetes	10	5.6	

This information sheds light on the sample population's health and demographic distribution, showing a preponderance of people with normal BMIs and lower income levels, as well as a significant percentage of people without comorbid diseases.

In our study there are total 179 patients out of which 74 are females (41.3%) and 105 males (58.7%).

The income, 108 people, or 60.3% of the total, make less than 50,000Rs in month. Just 2 members, or 1.1 percent, make more than 150,000 monthly, while 69 participants (38.5%) have monthly salaries between 50,000 and 150,000.

13 persons (7.3%) are classed as obese, while 166 people (92.7%) have a normal BMI. These numbers represent a sizable fraction of the sample. In terms of comorbidities, 136 individuals (76.0%) state they have no comorbid conditions. Of the people with comorbidities, 10 (5.6%) had diabetes, and 33 (18.4%) had hypertension (HTN).

[figure not shown]

Figure 1: Pie chart of patients using Silodosin and Tamsulosin (Medicine Advised)

Use of medicine (Figure 1)

Tamsulosin and Silodosin, the two drugs prescribed to a group of patients, are distributed as shown in the pie chart. Of the patients, 43% were advised to take Tamsulosin, which is shown as the blue section on the chart. And (57%) of the patients were advised to take silodosin, as shown by the red segment.

Table2: Patient demographic characteristics and study variables are

Varibales	Tamsulosin	Silodosin	p-value	
Body Mass index	Normal	72(43.4%)	94(56.6%)	0.730
	obese	5 (38.5%)	08(61.5%)	
Laterality	Right	65(55.6%)	52(44.4%)	0.001
	Left	12(19.4%)	50(80.6%)	
Symp To CT	Less than 1 week	67(64.4%)	37(35.6%)	
	More than 1 week	10(15.2%)	56(84.8%)	0.001
	More than 2 week	0 (0.0%)	09(100%)	
Posl n Ureler	Proximal	28(51.9%)	26(48.1%)	

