	Mid	08(17.4%)	38(82.6%)	0.001
	Distal	41(51.9%)	38(48.1%)	
Water intake	Less than 1 litre	59(54.6%)	49(45.4%)	
	More than 1 litre	18(25.4%)	53(74.6%)	0.001
Analgesic requirement	Yes	26(61.9%)	16(38.1%)	0.005
	No	51(37.2%)	86(62.8%)	
Time for removal	Less than 14 days	6(10.3%)	52(89.7%)	
	14-21	14(27.5%)	37(72.5%)	0.001
	22-28	57(81.4%)	13(18.6%)	

presented as frequency and percentage with association

The table compares several factors along with the corresponding p-values to assess statistical significance between two drugs tamsulosin and silodosin.

First, based on Body Mass Index (BMI), 43.4% of those with a normal BMI were prescribed Tamsulosin, while 56.6% were recommended Silodosin. On the other hand, among those who were obese, 38.5% were given Tamsulosin and 61.5% were given Silodosin; p-value came out to be 0.730, which meant that there was no statistically significant variation in the medication preferences according to BMI.

15.2% of patients who had pain for more than a week prior to CT scan, received Tamsulosin while 84.8% received silodosin.

51.9% of the patients with proximal ureteric stone were given Tamsulosin and 48.1% received Silodosin.

82.6 percent of patients with mid-ureteric stone problems received Silodosin, while 17.4% received Tamsulosin.

51.9% of patients with distal ureteric stones received Tamsulosin and 48.1% on Silodosin.

Only 38.1% of patients on Silodosin required analgesics, whereas 61.9% of patients on Tamsulosin used analgesics.

89.7% of patients on silodosin had their stone removed in less than 14 days, while only 10.3% of the patients on Tamsulosin had their stone removed in aforementioned duration.

72.5% of patients on Silodosin had their stone removed in 14-21 days, while only 27.5% of the patients on Tamsulosin had their stone removed in same duration.

Moreover, 81.4% on Tamsulosin had their stone removed in 22-28 days and 18.6% patients on Silodosin had it removed in same duration.

		Tamsulosin	Silodosin	p- value
Side	None	61 (40.1%)	91(59.9%)	
effect	Othostatic	09 (60.0%)	06(40.0%)	
	hypotension			0.3.15
	Abnormal	2(66.7%)	1(33.3%)	
	ejaculation			
	Headache	5(55.6%)	4 (44.4%)	

Table 2 Association between Tamsulosin and Silodosin with side effects

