The side effects that patients using silodosin and tamsulosin experienced are analyzed in the table, and the p-value denotes the statistical significance of these data. Patients on Silodosin, with no side effects were 59.9% while 40.1% on Tamsulosin did not report any side effects. This implies that, in comparison to Tamsulosin, Silodosin may have a marginally higher correlation with patients reporting no adverse effects.

Examining particular side effects reveals various themes. Nine patients on tamsulosin (60.0%) and six patients on silodosin (40.0%) developed orthostatic hypotension, a condition marked by a considerable drop in blood pressure upon

standing. It suggested that Tamsulosin users are more likely to have orthostatic hypotension than Silodosin users.

Only a very tiny percentage of patients reported abnormal ejaculation; 2 individuals on tamsulosin (66.7%) and 1 patient on silodosin (33.3%). Again, this points to an increased chance of this specific adverse effect in Tamsulosin users.

[figure not shown]
Another side effect that was identified involved headaches, which were seen by 4 individuals on silodosin (44.4%) and 5 patients on tamsulosin (55.6%). Headaches were marginally more common among Tamsulosin users compared to Silodosin users, similar to orthostatic hypotension.

None of the detected differences in side effect distribution between Tamsulosin and Silodosin is statistically significant, according to the p-value of 0.315. This implies that even if there are discernible variations in the frequency of particular adverse effects between the two drugs, these variations might just be the result of random variation rather than an actual distinction in the side effect profiles of tamsulosin and silodosin.

In conclusion, the analysis of side effects reveals that patients taking silodosin have a tendency to report no side effects more often than individuals taking tamsulosin. On the other hand, it seems that tamsulosin users are more likely to experience certain adverse effects, like headache, orthostatic hypotension, and abnormal ejaculation. Even with these findings, the absence of statistical significance suggests that more investigation using larger sample sizes would be necessary to conclusively identify any significant variations in the side effect profiles of Tamsulosin and Silodosin.

Figure 2

Bar Chart showing comparison of stone expulsion rate in Tamsulosin and

Silodosin groups

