For patients with ureteral stones (distal ureteral stones with a diameter of \geq 5 mm and \leq 10 mm), silodosin is very efficient in promoting stone expulsion with shorter expulsion times and fewer pain episodes. Additionally, it works well after lithotripsy to speed up stone movement and emphasize clearance rate(37). Dell'Atti L. evaluated the effectiveness of Tamsulosin and Silodosin in the ejection of 4–10 mm ureteral stones in distal parts of urethra. The research included 136 patients in total, all of whom were at least 18 years old. For three weeks, group 1 (67 patients) got 0.4 mg of tamsulosin daily, while group 2 (66 patients) received 8 mg of silodosin daily. Compared to Tamsulosin (61.2%, 41 out of 67 patients), patients treated with Silodosin experienced a statistically significant increase in the expulsion rate (80.3%, 53 out of 66); Silodosin also demonstrated a statistically significant advantage in terms of stone expulsion rate (p: 0.003) and expulsion time (weeks) (p: 0.002). There were no reported serious problems(42).

The rate and time of stone expulsion for both groups was evaluated using this method, as can be seen in Figure 2.

One main result of our study was 89.7% of patients on silodosin had their stone removed in less than 14 days, while only 10.3% of the patients on Tamsulosin had their stone removed in aforementioned duration. Also, 72.5% of patients on Silodosin had their stone removed in 14-21 days, while only 27.5% of the patients on Tamsulosin had their stone removed in same duration. Moreover, 81.4% on Tamsulosin had their stone removed in 22-28 days and 18.6% patients on Silodosin had it removed in same duration.

A similar meta analysis matched our results. Every study that was part of the analysis prescribed silodosin for at least two weeks. The results of several researches were compared by observing the effects of silodosin over a standardized period of time thanks to this constant timeframe. The results of this investigation showed that individuals with distal ureteral stones saw significantly higher rates of stone ejection when they received Silodosin for at least two weeks. This implies that silodosin worked well to help stones transit through the body in a short amount of time, which may lessen the need for more intrusive procedures and enhance patient outcomes when treating distal ureteral stones(43).

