Our Patients on tamsulosin accounted for 40.1% of those who did not report any side effects; those on silodosin made for a larger percentage (59.9%). This implies that, in comparison to Tamsulosin, Silodosin may have a marginally higher correlation with patients reporting no adverse effects.

There was no discernible difference in the reported orthostatic hypotension values of 3.6, 5.5, and 1.8% for the silodosin, tamsulosin, and placebo groups, respectively. Other side effects were noted in the silodosin, tamsulosin, and placebo groups, respectively, and included headache (3.6, 5.5, and 1.8%), dizziness (7.1, 10.9, and 3.6%), nasal congestion (1.8, 3.6, and 0), and nausea (1.8, 3.6, and 1.8%), all without a statistically significant difference. Based on the Common Terminology Criteria for Adverse Events, version 4.0, all cases were rated as grade 1(46).

The groups who took silodosin alone and the group that took silodosin plus tadalafil experienced similar side symptoms, such as headache, dizziness, backache, orthostatic hypotension, and retrograde ejaculation (Table-III). Given that P > 0.05, that was not statistically significant(41).

Examining particular side effects reveals various themes. Nine patients on tamsulosin (60.0%) and six patients on silodosin (40.0%) developed orthostatic hypotension, a condition marked by a considerable drop in blood pressure upon standing. Despite the fact that the sample size for this particular side effect is rather modest, it suggests that Tamsulosin users are more likely to have orthostatic hypotension than Silodosin users.

According to a study, the most common adverse event associated with the silodosin group was decreased or absent ejaculation. Of the patients in groups A and B, eight patients (8 were distressed, four were not, and six were distressed but could wait for their improvement) and nineteen patients (10 were distressed, four were not, and five were distressed but could wait for their improvement) experienced this adverse event most frequently(47).

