Only a very tiny percentage of patients reported experiencing abnormal ejaculation; 2 individuals on tamsulosin (66.7%) and 1 patient on silodosin (33.3%) reported this side event. Again, this points to an increased chance of this specific adverse effect in Tamsulosin users, but the numbers are too low to make any firm conclusions. Another side effect that was identified involved headaches, which were seen by 4 individuals on silodosin (44.4%) and 5 patients on tamsulosin (55.6%). Headaches were marginally more common among Tamsulosin users compared to Silodosin users, similar to orthostatic hypotension.

Many urologists agree when it comes to the incidence of retrograde ejaculation that it is an indication of therapy efficacy rather than a negative effect. It seems that silodosin relaxes the smooth muscles in the genital and lower urinary tracts sufficiently to cause a retrograde ejaculation. Retrograde ejaculation was more common in the individuals who experienced the most alleviation from lower urinary tract symptoms, which was consistent with this conclusion. This finding implies that the retrograde ejaculation is, in fact, a passive marker of the smooth muscle relaxation brought on by silodosin(32).

Typically, nonselective $\alpha 1$ adrenoceptor antagonists such doxazosin and terazosin are linked to orthostatic hypotension. Nonetheless, in clinical trials, silodosin was linked to a modest incidence of orthostatic hypotension. According to the combined analysis of the US and European studies, 1.1% of patients receiving a placebo and 1.3% of patients receiving silodosin experienced orthostatic hypotension(48).

When compared to Tamsulosin, Silodosin is linked to a larger incidence of retrograde ejaculation but a reduced incidence of peripheral vasodilation-related adverse effects, such as orthostatic hypotension and dizziness, according to a retrospective review conducted by Imperatore et al(49).

In our study comparing the effects of Tamsulosin and Silodosin on patients, it was discovered that only 38.1% of those receiving Silodosin needed analgesics to ameliorate ureteric pain. On the other hand, 61.9% of patients receiving Tamsulosin required analgesic intervention, which is a far larger percentage. This significant difference raises the possibility that silodosin is more successful in treating ureteric stones and it also lowers their need for extra painkillers.

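### Results text reports row shares as rates within each arm: 89.7% v 10.3% for stone removal in under 14 days, where the table counts give 51.0% v 7.8% of tabulated patients

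*Combined protocol and SAP*

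**What the plan says.** In the Results, two tables are both labelled Table 2: one for patient characteristics and study variables, one for side effects. In both, the two percentages in each row add to 100% across the drugs. The text then uses these figures as follows.

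- Removal under 14 days: "89.7% of patients on silodosin had their stone removed in less than 14 days, while only 10.3% of the patients on Tamsulosin". The 14-21 day figures (72.5% and 27.5%) are worded the same way.
- Removal at 22-28 days: "Moreover, 81.4% on Tamsulosin had their stone removed in 22-28 days and 18.6% patients on Silodosin had it removed in same duration".
- Analgesics: "Only 38.1% of patients on Silodosin required analgesics, whereas 61.9% of patients on Tamsulosin used analgesics".
- No side effects: "Patients on Silodosin, with no side effects were 59.9% while 40.1% on Tamsulosin did not report any side effects".

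The Discussion repeats the first figure ("One main result of our study was 89.7% of patients on silodosin had their stone removed in less than 14 days") and the analgesic figure ("only 38.1% of those receiving Silodosin needed analgesics to ameliorate ureteric pain"). It words the side-effect figure correctly, as a share of those free of side effects: "Our Patients on tamsulosin accounted for 40.1% of those who did not report any side effects". The sentences on BMI, time from symptoms to CT and stone position also read the row shares correctly.

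The tabulated arms are unequal. For Figure 1 the text says "Of the patients, 43% were advised to take Tamsulosin, which is shown as the blue section on the chart", with 57% on silodosin.

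**The concern.** A row share answers the question: of the patients with this outcome, what fraction took silodosin? A reader of an efficacy result wants the other conditional: of the patients on silodosin, what fraction had the outcome? The sentences listed above give the first and word it as the second.

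Two things follow. The treatment differences come out at the wrong size, most of all for early removal. And a row share carries the arm sizes: with 43% of patients on one drug and 57% on the other, it shows a gap even where the drugs do not differ.

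The Discussion sets 89.7% v 10.3% shortly after a cited trial's true arm rates for the same two drugs (53 of 66, 80.3%, v 41 of 67, 61.2%), which invites comparison of unlike quantities.

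**Working it through.** **Inputs** (counts from the two Results tables, tamsulosin / silodosin)

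- Removal: under 14 days 6 / 52; 14-21 days 14 / 37; 22-28 days 57 / 13
- Analgesic required: yes 26 / 16; no 51 / 86
- Side effects: none 61 / 91; orthostatic hypotension 9 / 6; abnormal ejaculation 2 / 1; headache 5 / 4

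**Arm totals.** Each block gives the same sums: 6+14+57 = 26+51 = 61+9+2+5 = 77, and 52+37+13 = 16+86 = 91+6+1+4 = 102. Together 77 + 102 = 179, the total given in the Results, and 77/179 = 43.0%, 102/179 = 57.0%, the Figure 1 split.

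**Reproducing the stated figures.** Row share = arm count / row total: 52/58 = 89.7%, 6/58 = 10.3%; 37/51 = 72.5%, 14/51 = 27.5%; 57/70 = 81.4%, 13/70 = 18.6%; 26/42 = 61.9%, 16/42 = 38.1%; 91/152 = 59.9%, 61/152 = 40.1%. All match.

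**Can they be arm rates?** The removal windows are mutually exclusive, so rates within an arm cannot exceed 100% in total. As worded, silodosin gives 89.7 + 72.5 + 18.6 = 180.8% and tamsulosin 10.3 + 27.5 + 81.4 = 119.2%. This needs no assumption about arm size.

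**Arm rates from the counts.** Rate = count / arm total. Difference d = silodosin minus tamsulosin. Wald 95% CI = d ± 1.96 × √(p₁(1−p₁)/102 + p₂(1−p₂)/77). For under 14 days: 0.510 − 0.078 = 0.432, standard error 0.058, giving 31.8 to 54.6 points.

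| Outcome | Silodosin (102) | Tamsulosin (77) | Difference, points (95% CI) | Gap as worded |
|---|---|---|---|---|
| Removed <14 days | 51.0% | 7.8% | +43.2 (31.8 to 54.6) | +79.4 |
| Removed 14-21 days | 36.3% | 18.2% | +18.1 (5.4 to 30.8) | +45.0 |
| Removed 22-28 days | 12.7% | 74.0% | −61.3 (−73.0 to −49.5) | −62.8 |
| Analgesic required | 15.7% | 33.8% | −18.1 (−30.8 to −5.4) | −23.8 |
| No side effect | 89.2% | 79.2% | +10.0 (−0.9 to 20.9) | +19.8 |

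**Effect of arm size.** If both drugs had the same side-effect rate, the no-side-effects row would still print 57.0% v 43.0%, a gap of 14.0 of the 19.8 points.

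**Are the counts sound?** Pearson chi-square gives p = 0.0047 for analgesics (printed 0.005) and 3.54 on 3 df, p = 0.315, for the four side-effect categories (text 0.315).

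**Other denominators.** The abstract's 93 silodosin patients cannot contain the 102 tabulated. On the 104/104 randomised, assume the table labels are the randomised arms and let the 27 and 2 untabulated patients be all non-events or all events:

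- Under 14 days: silodosin 52/104 to 54/104 (50.0% to 51.9%); tamsulosin 6/104 to 33/104 (5.8% to 31.7%); difference +18.3 to +46.2 points.
- Analgesics: silodosin 16/104 to 18/104 (15.4% to 17.3%); tamsulosin 26/104 to 53/104 (25.0% to 51.0%); difference −35.6 to −7.7 points.

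Neither the 89.7% for silodosin nor the 38.1% and 61.9% for analgesics lies in its range. The 10.3% for tamsulosin does.

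**Safety.** The complement of the no-side-effect row is 11/102 (10.8%) v 16/77 (20.8%): −10.0 points (−20.9 to 0.9), Pearson p = 0.064, Fisher p = 0.090.

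**The case against.** The strongest reply is that this is a wording error with little consequence. The correct counts stand in the same table. No direction or count-based p-value changes. The abstract gives counts for removal time, the Conclusion gives no percentages, and the 22-28 day gap hardly moves. For analgesics the ratio of tamsulosin to silodosin even rises, from 61.9/38.1 = 1.62 to 33.8/15.7 = 2.15. All of this is true and limits the harm. It does not rescue a figure that the Discussion presents as a main result and that the same table contradicts.

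The no-side-effects sentence is the loosest in wording, and its first half could be read as a row share. Its second half, on tamsulosin, cannot.

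The counts themselves are not fully consistent. The Figure 2 text gives about 55 v 5 (silodosin v tamsulosin) for under 14 days and about 30 v 20 for 14-21 days, against 52 v 6 and 37 v 14 in the table. These are approximate chart readings, and the table's analgesic and side-effect counts reproduce their printed p-values, so the table is the better source. The discrepancy still needs clearing up.

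Finally, the 104/104 bounds hold only under their stated assumption, and the two-category side-effect test was not planned. Neither is needed for the main point, which rests on the window totals.

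**Conclusion.** The concern holds. The removal-time, analgesic and no-side-effects sentences state row shares as rates within each arm. For early removal this turns 51.0% v 7.8% into 89.7% v 10.3% and a 43.2-point difference into 79.4. That the figures are not arm rates follows from the window totals alone. The replacement values rest on the tabulated totals of 77 and 102 and describe tabulated patients only, not all who were randomised.

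The abstract has a further instance: orthostatic hypotension is printed as 60.0% v 40.0% (tamsulosin v silodosin), where the counts give 9/77 = 11.7% v 6/102 = 5.9%.

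A separate, secondary point is one of overclaim rather than arithmetic. The abstract and Conclusion say without qualification that silodosin is the safer drug, while the Results report no significant difference (p = 0.315) and the Discussion hedges on small numbers.

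**What to change.** 1. Reconcile the arm sizes: 104/104 randomised; 89/93 in the abstract, which sum to 182 against a stated 180; 77/102 in the tables. Reconcile the Figure 2 text with the table counts. State how many patients did not pass the stone, since every tabulated patient has a removal window.
2. Report each outcome as n/N over the arm total, with a risk difference and 95% CI, in the Results, Discussion and abstract. For example: *Among tabulated patients, 52 of 102 on silodosin (51.0%) and 6 of 77 on tamsulosin (7.8%) had their stone removed in less than 14 days (difference +43.2 points, 95% CI 31.8 to 54.6).* Do not use 89/93 as denominators. If 104/104 is used, say how untabulated patients are counted.
3. Separately, replace the safety claims with, for example: *Among tabulated patients, any side effect was reported by 11/102 (10.8%) on silodosin and 16/77 (20.8%) on tamsulosin (difference −10.0 points, 95% CI −20.9 to 0.9; four-category p = 0.315). No statistically significant difference was shown; this does not establish equal safety.* If the two-category p-values (Pearson 0.064, Fisher 0.090) are added, label them as not prespecified.

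The cost is recomputing percentages from printed counts and rewording. The reconciliation in step 1 is the only part that needs the trial records.

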It is hypothesized that efficacy and safety of medical expulsive therapy, containing tamsulosin and silodosin, is almost the same and silodosin can be used with the same efficacy for the treatment of lower urinary tract calculi.

Alternative Hypothesis:

Silodosin is better than Tamsulosin in efficacy and safety.

OPERATIONAL DEFINITIONS:

STONE CLEARANCE:

Stone clearance will be defined as no evidence of stone on follow up X-ray KUB imaging at 4 weeks .

ANCILLARY PROCEDURES:

Additional urological procedures needed to remove the same stone for which medical expulsive therapy was given if it fails to remove the stone completely.

SIDE EFFECTS:

Any undesirable effect noticed after prescription of the drug including but not limited to abnormal ejaculation, headache, orthostatic hypotension, backache and gastritis etc.

MATERIALS AND METHODS:

STUDY DESIGN:

Prospective randomized control trial.

STUDY SETTING:

Outpatient department of Sir Ganga Ram hospital, Lahore.

DURATION OF STUDY:

18 months.

DURATION OF TREATMENT:

Four weeks.

SAMPLE SIZE:

Using the open-epic software, the sample size was estimated. The minimum sample size that we require is 208 patients with ureteric stone who fulfil the inclusion criterion with 104 in one group receiving tamsulosin and 104 in silodosin group (1:1 ratio) with an inflation of 10 percent for estimated loss to follow up, with an anticipated expulsion rate ranging from 58-64 percent in tamsulosin group and 78-83 percent in silodosin group with a risk difference of 19 to achieve a power of 80 percent and a level of significance of 5 percent.

SAMPLING TECHNIQUE:

Patients visiting the outpatient department of Sir Ganga Ram hospital will be selected by simple random sampling, fulfilling the inclusion criteria.

SAMPLE SELECTION:

Adult male and female patients fulfilling the inclusion criteria will be assigned into two groups by random allotment, 1^{st} group will be given Tamsulosin and 2^{nd} group will be given Silodosin for four weeks.

INCLUSION CRITERIA:

Following factors make up the inclusion criteria for this study.

- Patients between ages 18 years 55 years.
- Solitary unilateral ureteral stone
- Stone sizes less than 10 mm measured on non-contrast computed tomography of kidney, ureter and bladder.
- Stones being treated primarily with medical expulsive therapy
- Radio opaque Stone

EXCLUSION CRITERIA:

The presence of following factors will exclude the patients from our study:

- Pregnancy
- Untreated UTI

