Similar results were seen in another study showing that, individuals receiving just tamsulosin treatment needed a greater average analgesic dosage of 391.43 \pm 165.60 mg with a p-value of 0.005, which denotes substantial significance, the necessary(50).

Similarly, a study showed statistically significant difference in the amount of analgesics needed by patients treated with Silodosin compared to those treated with tamsulosin only. The robustness of the conclusion was highlighted by the fact that the group receiving Silodosin treatment required considerably fewer analgesics than the groups receiving Tamsulosin, with a p-value of < 0.001(51).

Conclusion

An effective treatment for ureteral stones is medical expulsive therapy. According to our findings, silodosin has a safer profile and is more successful than tamsulosin at ejecting ureteric stones.

Silodosin had an increased rate of stone expulsion and took less time in stone expulsion compared to those treated with Tamsulosin.

In addition, patients treated with silodosin reported fewer side effects, such as a retrograde ejaculation, orthostatic hypotension and headaches as compared to those taking Tamsulosin.

In addition, those who received Silodosin needed less analgesic medication than those who received Tamsulosin.

•

REFERENCES

- Ahmed AFAM, Al-Sayed AYS. Tamsulosin versus Alfuzosin in the Treatment of Patients with Distal Ureteral Stones: Prospective, Randomized, Comparative Study. Korean J Urol. 2010 Mar;51(3):193–7.
- 5. Pietropaolo A, Proietti S, Geraghty R, Skolarikos A, Papatsoris A, Liatsikos E, et al. Trends of 'urolithiasis: interventions, simulation, and

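### Abnormal ejaculation is reported as shares of three events, with women in the table and no sex-by-arm count, yet the Conclusion lists it as less frequent with silodosin

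*Combined protocol and SAP*

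**What the plan says.** Under Sample Selection both sexes are eligible: "Adult male and female patients fulfilling the inclusion criteria will be assigned into two groups by random allotment". The Results report the sex split for the trial as a whole: "In our study there are total 179 patients out of which 74 are females (41.3%) and 105 males (58.7"%). Sex is not broken down by arm.

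The side-effect table in the Results treats the side effect as one variable with four categories (none, orthostatic hypotension, abnormal ejaculation, headache) and gives one p-value, 0.315. On ejaculation the text says: "Only a very tiny percentage of patients reported abnormal ejaculation; 2 individuals on tamsulosin (66.7%) and 1 patient on silodosin (33.3"%). It then infers: "Again, this points to an increased chance of this specific adverse effect in Tamsulosin users".

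Two later statements limit that inference. The Results say that no difference in side-effect distribution is significant, and the Discussion says of this event that the counts are too small for firm conclusions. The Conclusion carries neither limit. It says that "patients treated with silodosin reported fewer side effects, such as a retrograde ejaculation, orthostatic hypotension and headaches", compared with tamsulosin, and it describes silodosin's profile as safer.

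**The concern.** Three things are wrong with how this event is reported.

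- **The percentages are not risks.** They show how three events divide between the drugs. With arms of 77 and 102, an equal risk per patient would not give a 50/50 split, so these shares cannot be compared with each other as rates.
- **The denominator includes people not at risk.** Women make up 41.3% of the analysed patients and cannot have the event, but they are in the table and in its test.
- **Men per arm are not given.** A reader cannot compute the rate among those at risk in either arm.

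The stake is a safety statement. Comparing side-effect profiles is a stated objective, and the Conclusion presents ejaculatory effects as an advantage of silodosin. The document's own literature points the other way: the Literature Review describes a meta-analysis in which silodosin raised the incidence of retrograde ejaculation, and the Discussion cites a retrospective review with the same direction. A finding against that background needs a proper at-risk denominator and an interval. The Conclusion also says retrograde ejaculation, whereas the category recorded in the table is abnormal ejaculation.

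**Working it through.** **Inputs**

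- Sex: 105 men and 74 women, total 179 (Results, demographic data).
- Side-effect table, tamsulosin / silodosin: none 61 / 91; orthostatic hypotension 9 / 6; abnormal ejaculation 2 / 1; headache 5 / 4.
- Men per arm: not given. This is an assumption below.

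**Step 1: who is in the table.** Tamsulosin: 61 + 9 + 2 + 5 = 77. Silodosin: 91 + 6 + 1 + 4 = 102. Sum: 179, so all 74 women are included.

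**Step 2: reproduce the printed figures.** Pearson chi-square = Σ(observed − expected)²/expected over the 4 × 2 table, where expected = row total × column total / 179. For example, ejaculation on tamsulosin has expected count 3 × 77/179 = 1.29. The sum is 3.543 on 3 degrees of freedom, p = 0.3152, which matches the printed 0.315. The shares also reproduce: 2/3 = 66.7% and 1/3 = 33.3%.

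**Step 3: incidence overall**

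- All patients: 3/179 = 1.7%.
- Men only: 3/105 = 2.9%, exact (Clopper-Pearson) 95% CI 0.6% to 8.1%.

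**Step 4: incidence by arm over all patients.** 2/77 = 2.6% and 1/102 = 1.0%; Fisher exact p = 0.58.

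**Step 5: incidence by arm among men, proportional split assumed.** Men on tamsulosin: 77 × 105/179 = 45.2, taken as 45. Men on silodosin: 102 × 105/179 = 59.8, taken as 60.

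- Tamsulosin: 2/45 = 4.4%, exact 95% CI 0.5% to 15.1%.
- Silodosin: 1/60 = 1.7%, exact 95% CI 0.04% to 8.9%.
- Fisher exact p = 0.58, as in Step 4.

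**Step 6: other splits of the 105 men**

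| Men on tamsulosin / silodosin | Tamsulosin | Silodosin | Fisher p |
|---|---|---|---|
| 35 / 70 | 5.7% | 1.4% | 0.26 |
| 45 / 60 | 4.4% | 1.7% | 0.58 |
| 55 / 50 | 3.6% | 2.0% | 1.0 |
| 70 / 35 | 2.9% | 2.9% | 1.0 |
| 77 / 28 | 2.6% | 3.6% | 1.0 |

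The feasible range for tamsulosin is 3 to 77 men, since silodosin has at most 102 and 105 − 102 = 3. The direction reverses only at 71 or more men among the 77. The p-value falls below 0.05 only at 14 or fewer.

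**Step 7: how plausible the extremes are.** If the 105 men were allocated at random among 179 patients, the number in an arm of 77 is hypergeometric with mean 45.2 and SD 3.3. The probability of 71 or more is about 1e-16.

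**The case against.** The case for leaving this alone has four parts.

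**No printed rate is too low.** A reader might infer that the trial understates the ejaculation rate 1.7-fold, from 2.9/1.7. The documents do not support that: neither 3/179 nor any per-arm incidence is printed. The only wording that leans on all patients is the phrase about a very tiny percentage, which fits 2.9% about as well as 1.7%. This part stands.

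**The direction is not in real doubt.** A reader might also infer that correcting for sex could turn the comparison round. It could do so only if at least 71 of the 77 tamsulosin patients were men. Laterality, symptom duration and stone position differ between arms at a reported p = 0.001, so balance on sex cannot be taken for granted. Still, nothing in the documents suggests an arm that is at least 92% male (71/77). This part stands too.

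**The row percentages are not special to this event.** The same layout is used for hypotension ("Nine patients on tamsulosin (60.0%) and six patients on silodosin (40.0%) developed orthostatic hypotension"), for headache, for analgesic use and for time to expulsion. That is so, but it does not make the ejaculation figures right, and the male-only denominator is an additional fault of this row.

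**The text already disclaims the inference.** The Results and the Discussion both do. The Conclusion does not, and it is the part most likely to be read alone. This objection explains why the fix is small; it does not remove the need for it.

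**Conclusion.** The point holds as a reporting fault and an unsupported statement in the Conclusion. The printed 66.7% and 33.3% are not incidences, women are counted in a comparison they cannot contribute to, and sex by arm is missing. The rate among those at risk is 2.9% (0.6% to 8.1%), a figure that needs no assumption beyond the printed counts.

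The per-arm figures, 4.4% and 1.7%, rest on an assumed proportional split of men. Over 35 to 55 men on tamsulosin, p runs from 0.26 to 1.0, so under any roughly balanced split three events show no difference between the drugs. Changing the denominator does not by itself change the test result, and efficacy results are untouched. What does need to change is the claim that silodosin reduced retrograde ejaculation, which 2 events against 1 cannot carry and which the document's own Results and Discussion do not back.

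**What to change.** 1. Report the number of men and women in each arm.
2. Replace the shares of events with n/men in each arm and an exact 95% CI for each arm, and say that the denominator is men.
3. In the Conclusion, remove retrograde ejaculation from the list of effects less frequent with silodosin, or state there that three events cannot show a difference. If the term stays, use the category that was recorded, abnormal ejaculation.
4. Bring the sentence in the Results that infers a higher chance with tamsulosin into line with the caveat in the Discussion.

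The cost is one re-tabulation of sex, which was already collected, and edits to two sentences. No new data are needed.
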